6.1 Potential Risks

The potential risks and complications of the device will be explained to the patients receiving the implanted device. The risks similar to the risks of other devices approved for endovascular aneurysm treatment are well known.

| Cerus Endovascular | Document Number DNX099-01 | Rev F | Page 26 of 106 |
|----------------------------|--|----------|----------------|
| Investigational Protocol | Title | | |
| Confidential & Proprietary | Contour Neurovascular System TM European Pre-Market Unruptured Aneurys Study (CERUS) | | ured Aneurysm |

These risks may cause significant neurologic complications such as a cerebrovascular accident (CVA) and possibly death, and include but are not limited to the following: infection, abnormal bleeding or clotting, pain, injury to the groin site, injury to the aneurysm including bleeding and/or rupture, decreased blood flow to the brain or other parts of the body, inability of the device to totally prevent blood from flowing inside it, movement of the device within the aneurysms or to another location in the body.

| Anticipated Risk by Clinical Category | Percent Anticipated Risk Occurence | Specific Anticipated Risks |
|---|--|----------------------------|
| Neurovascular Sequelae | Rarely (< 5%) | CVA – ischemic |
| * | Rarely (< 5%) | CVA – hemorrhagic |
| | Rarely (< 5%) | Aneurysm rupture |

| Anticipated Risk by Clinical Category | Percent Anticipated Risk Occurence | Specific Anticipated Risks |
|---|--|---|
| | Rarely (< 5%) | Blood vessel dissection |
| | Rarely (< 5%) | Blood vessel perforation/rupture |
| | Rarely (< 5%) | Subarachnoid hemorrhage |
| | Rarely (< 5%) | Parenchymatous hematoma |
| | Rarely (< 5%) | Intraventricular hemorrhage |
| | Rarely (< 5%) | Thrombosis with resultant occlusion of aneurysm parent artery of other blood vessel |
| | Rarely (< 5%) | Embolism with resultant occlusion of blood vessel |

| Cerus Endovascular | Document Number DNX099-01 | Rev F | Page 27 of 106 |
|----------------------------|--|---------------|----------------|
| Investigational Protocol | Title | | |
| Confidential & Proprietary | Contour Neurovascular System TM European Pre-M Study (CERUS) | larket Unrupt | ured Aneurysm |

| | Less Likely (5-15%) | Device migration – from the aneurysm to a distal site |
|---|--|---|
| | Likely (>15%) | Headache |
| | Rarely (< 5%) | Cranial nerve palsy |
| | Rarely (< 5%) | Intra-cranial hypertension |

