Two patient populations will be considered in the analyses, an Intent-to-Treat (ITT) population and a Per Protocol population (PP). The ITT population includes all patients. The PP population will include subjects who complete 6 months of follow-up, die prior to their 6-month clinic visit, or are study failure (withdrawal from study to obtain alternate treatment). The PP will exclude patients with any major protocol violation that affects proper study inclusion or significant outcomes. Endpoints will be evaluated in the PP and ITT populations.

Any patient for whom a failed implant attempt is performed will be followed for 1 month, or until resolution of any potential device or implanted related adverse events, whichever occurs last.

Any patient who is consented but has no implant attempt will be study exited.

6 General Statistical Principles

The analysis for all primary and secondary study endpoints and baseline, procedural and follow-up characteristics will be performed on an intent-to-treat analysis population which will include all available data for all enrolled subjects. Standard summary statistics will be calculated for all study variables. For continuous variables, statistics will include means, standard deviations, medians and ranges. Categorical variables will be summarized in frequency distributions. Missing data will not be imputed. The number of data values available for each analysis will be reported so that the impact of missing data can be seen.

Statistical analyses will be conducted in SAS version 9.4 or above (SAS Institute, Cary, N.C.).

Cerus Endovascular	Document Number DNX099-13	Rev A	Page 7 of 9	
Statistical Analysis Plan	Title Statistical Analysis Plan for: Contour Neurovascular System [™] European PreMarket Unruptured Aneurysm Study (CERUS)			
Confidential & Proprietary				

7 Analysis of Study Endpoints

Primary Safety Endpoint

The primary safety endpoint will be calculated as the proportion of subjects with death of any nonaccidental cause or any major disabling stroke within the first 30 days after treatment or major disabling stroke or death due to neurological cause from day 31 to 6 months after treatment.

Where "Major Disabling Stroke" is defined as an episode of neurological signs or symptoms that persist beyond 24 hours accompanied with evidence of ischemia/infarction on imaging that results in an increase of NIHSS from baseline by ³ 4 points and/or an increase from mRS baseline by >2.

Primary Performance Endpoint

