The primary performance endpoint will be calculated as the proportion of subjects with complete occlusion demonstrated with a Grade 1 on the Raymond Roy Scale at 6 months. The data will be as reported as analyzed by the core laboratory.

Secondary Safety Endpoints

- Serious Adverse Events (SAE) associated with the procedure or device will be calculated as the proportion of subjects with at least one SAE and each individually reported SAE. Event counts will also be reported.
- Serious neurological adverse events will be calculated as the proportion of subjects with at least one serious neurological AE and each individually reported neurological AE. Event counts will also be reported.

Secondary Performance Endpoints

The secondary performance endpoints will be reported as analyzed by the core laboratory. The endpoints will be analyzed at the the 6-month post implant timepoint unless procedure-related.

- Raymond Roy scale: the endpoint will be calculated as the proportion of subjects with each category
- Modified Web occlusion scale: the endpoint will be calculated as the proportion of subjects with each category

Cerus Endovascular	Document Number DNX099-13	Rev A	Page 8 of 9	
Statistical Analysis Plan	Title Statistical Analysis Plan for: Contour Neurovacular System TM European			
Confidential & Proprietary	PreMarket Unruptured Aneurysm Study (CERUS)			

- Percent occlusion: the endpoint will be calculated as the mean and standard deviation or median and range depending on the normality of the data of the measured occlusion
- Device stability: the endpoint will be calculated as the proportion of subjects with stable device placement
- Retreatment: the endpoint will be calculated as the proportion of subjects with retreatment of the target aneurysm between the implant procedure and 6 month post implant timepoint
- Time required for implantation of the Contour: the endpoint will be calculated as the mean and standard deviation or median and range depending on the normality of the data
- Device size: the endpoint will be calculated as the proportion of subjects with each size of implanted Contour device
- Number of attempts to deploy the device: the endpoint will be calculated as the proportion of subjects with each number of implant attempts (e.g. 1, 2, 3)
- Number of failed attempts to deploy the device: the endpoint will be calculated as the proportion of subjects with each number of failed attempts (e.g. 1, 2, 3)

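### Device stability is a 6-month status on available data with no denominator or failure rule, so instability followed by exit or death before the 6-month DSA is left out and the rate is biased upward

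*SAP*

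**What the plan says.** SAP section 7 gives one timing rule for the secondary performance endpoints: "The endpoints will be analyzed at the the 6-month post implant timepoint unless procedure-related". They are reported as read by the core laboratory. The entry for this endpoint is "Device stability: the endpoint will be calculated as the proportion of subjects with stable device placement". It does not say what makes a placement stable, who is in the denominator, or how a device that moved before 6 months is scored.

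SAP section 6 sets the analysis population as one "which will include all available data for all enrolled subjects". It adds "Missing data will not be imputed" and "The number of data values available for each analysis will be reported so that the impact of missing data can be seen". Protocol section 7.9 and the schedule of assessments plan a single follow-up DSA, at 6 months.

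Three other places bear on the point:

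- SAP section 5 keeps in the per-protocol population subjects who die before the 6-month visit "or are study failure (withdrawal from study to obtain alternate treatment"). It assigns them no stability outcome.
- SAP section 7 counts a neighbouring endpoint over the whole interval: "Retreatment: the endpoint will be calculated as the proportion of subjects with retreatment of the target aneurysm between the implant procedure and 6 month".
- Protocol section 6.1 lists "Device migration – from the aneurysm to a distal site" with an anticipated occurrence of 5-15%.

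**The concern.** Loss of stability is an event that can happen at any time after detachment. A status at one later date, computed on available readings, measures it fully only if everyone whose device moved still has that reading. Those who leave because the device failed are the ones least likely to have it. The SAP foresees such exits and gives them no stability outcome.

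Stability is a central performance claim here. The protocol synopsis says the device does not rely on the aneurysm dome to hold it and needs no anchoring in the parent vessel. Protocol section 4 faults another intrasaccular device for migration and compaction. A stability rate that omits some of the failures it is meant to count would support that claim more strongly than the data do. With about 30 subjects, each omitted failure moves the rate by roughly 3 points.

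**Working it through.** The plan states no expected stability rate, alpha, power or formal sample size, so there is no figure of its own to reproduce. The check compares two rates: (A) stable among subjects with a 6-month reading, which is what the SAP text yields, and (B) stable among all implanted subjects, with early instability kept as failure.

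**Inputs**

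- Migration risk p: 5-15% (protocol section 6.1). This covers migration to a distal site only. Other displacement would add to it.
- Implanted subjects: 35, assumed. This is the maximum enrolment in the synopsis, and the implanted number could be lower.
- Share f of migrators without a 6-month reading: not in the documents, so shown from 0 to 1.
- Also assumed: every non-migrated device is read as stable, and a migrator who does have the DSA is scored not stable.

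**How many migrations to expect**

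35 × 0.05 = 1.75 and 35 × 0.15 = 5.25. The chance of at least one is 1 − 0.95^35 = 83% at the low end and 1 − 0.85^35 = 99.7% at the high end.

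**Expected overstatement**

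Rate B is 1 − p. Rate A is (1 − p) / [(1 − p) + p(1 − f)].

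| p | f | B | A | A − B (points) |
|---|---|---|---|---|
| 5% | 0 | 95.0% | 95.0% | 0 |
| 5% | 0.5 | 95.0% | 0.95/0.975 = 97.4% | 2.4 |
| 5% | 1 | 95.0% | 100% | 5.0 |
| 15% | 0 | 85.0% | 85.0% | 0 |
| 15% | 0.5 | 85.0% | 0.85/0.925 = 91.9% | 6.9 |
| 15% | 1 | 85.0% | 100% | 15.0 |

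**In counts, with 35 implanted and m unstable devices lost before the DSA (exact 95% CI)**

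| m | SAP rate | All implanted | Gap (points) |
|---|---|---|---|
| 1 | 34/34 = 100% (89.7-100) | 34/35 = 97.1% (85.1-99.9) | 2.9 |
| 3 | 32/32 = 100% (89.1-100) | 32/35 = 91.4% (76.9-98.2) | 8.6 |
| 5 | 30/30 = 100% (88.4-100) | 30/35 = 85.7% (69.7-95.2) | 14.3 |

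The last row is the extreme in which the whole attrition allowance (35 − 30 = 5) consists of early unstable devices. The direction is fixed: removing a failure from the denominator can only raise a rate that is below 100%. The size is not fixed.

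**The case against.** Several stronger readings are tempting, and the documents do not support them.

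- A reader might infer that retreated subjects drop out of the stability rate. They do not automatically do so. The protocol synopsis has all implanted subjects complete the scheduled assessments, and section 7.10 does not list retreatment as a reason for withdrawal. What is missing is a scoring rule. A subject retreated for instability could be called not stable, stable after retreatment, or not assessable.
- A reader might infer that a 6-month reading hides early migration. Under protocol section 7.6.1, procedure-day imaging is the core-lab baseline for the 6-month comparison, so a device still displaced at the 6-month DSA would be seen. Protocol section 10.5.2 and the SAP synopsis also describe the core-lab assessment as running from post-procedure to 6 months. The SAP section 7 rule is narrower, but that wording shows a wider intent.
- A reader might infer that early instability would surface only as an adverse event. It may also show in the retreatment rate, the device-deficiency proportion, the discontinuation summary and the subject listings (SAP sections 7 and 8). The number of available values is printed beside each analysis.
- A reader might set 27/27 = 100% against 27/30 = 90% as the expected effect. That assumes every migrator leaves. It also takes losses out of 30, which protocol section 10.7 gives as the target number with evaluable 6-month data.

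These points limit the size and make the loss partly visible. None of them corrects the stability rate itself or ties a missing reading to the reason it is missing. The endpoint is also secondary and descriptive, with no hypothesis test, so no error rate or success criterion depends on it.

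**Conclusion.** The point holds in a limited form. As written, the SAP yields an upward-biased stability rate whenever a device becomes unstable and the subject exits or dies before the 6-month DSA, and it leaves the scoring of retreatment for instability open. At 5-15% migration risk the expected overstatement runs from 0 (every migrator has the DSA and is scored not stable) to 5-15 points (none has it), with 2.4 to 6.9 points if half are missing. The share f is an assumption, and the documents support no particular value. It is therefore not established that the rate will be overstated, only that the rule permits it and that the error can go only one way. This should be corrected before analysis, but it does not threaten the primary endpoints.

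**What to change.** Replace the device-stability entry in SAP section 7 with a cumulative definition:

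- **Criterion.** Define stable as no migration or movement from detachment through the 6-month DSA. Define both terms; protocol section 4 already separates them when discussing another device.
- **Denominator.** All subjects with an implanted (detached) Contour.
- **Failure.** Documented instability at any earlier time, or retreatment or exit because of instability, counts as not stable whether or not a 6-month reading exists.
- **Sources.** Use core-lab reads of scheduled and unscheduled imaging. Where no core-lab read exists, supplement with CEC-adjudicated adverse event and device-deficiency records. State which source governs if they disagree.
- **Display.** Give the 6-month status as a secondary line. Show readings missing for other reasons separately, with best-case and worst-case bounds. For example, with 30 of 35 read and all 30 stable, the bounds are 35/35 = 100% and 30/35 = 85.7%.

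No new data collection is needed. Protocol section 7.9 already sends all angiographic images to the core laboratory, and section 8.1 already puts adverse events and deficiencies on case report forms. The cost is a short SAP amendment, a stability figure that may be slightly less favourable, and an endpoint that no longer rests on core-lab reads alone.
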